9.1.2.2. Laboratory data

Missing laboratory results (including immunological data) will not be replaced.

9.1.2.3. Daily recording of solicited symptoms

For studies using paper diaries which have questions in the CRF indicating the presence or absence of solicited symptoms, the following rules are applicable.

Denominators for the summary of local (or general) solicited symptoms will be calculated using the number of subjects who respond “Yes” or “No” to the question concerning the occurrence of local (or general) symptoms.

When a specific symptom is marked as having not occurred following a specific vaccination (i.e. SDTM CE.CEOCCUR=N for the specified post-vaccination period for the symptom in question), all daily measurements will be imputed as Grade 0.

When a specific symptom is marked as having occurred following a specific vaccination (i.e. SDTM CE.CEOCCUR=Y for the specified post-vaccination period for the symptom in question), any missing daily recordings will be given imputed values to allow them to contribute to the ‘Any’ rows but not to specific grade rows of the symptom summary tables.

When the occurrence of a specific symptom is not present (i.e. SDTM CE.CEOCCUR is neither Y nor N for the specified post-vaccination period for the symptom in question) but the group of symptoms (local or general) is marked as having occurred (i.e. SDTM CE.CEOCCUR=Y), all missing daily recordings will be given imputed values to allow them to contribute to the ‘Any’ rows but not to specific grade rows of the symptom summary tables.

The following table shows how subjects contribute to each category for a specific solicited symptom over the Day X to Day Y post-vaccination period:

Solicited symptom category	Subjects included in the calculation of the numerator
Any	All subjects with at least one occurrence of the symptom at grade 1, grade 2, or grade 3 between Day X and Day Y or with the symptom marked as present and at least one missing daily recording between Day X and Day Y
At least grade 1	All subjects with at least one occurrence of the symptom at grade 1, grade 2, or grade 3 between Day X and Day Y
At least grade 2	All subjects with at least one occurrence of the symptom at grade 2 or grade 3 between Day X and Day Y
At least grade 3	All subjects with at least one occurrence of the symptom at grade 3 between Day X and Day Y

9.1.2.4. Unsolicited adverse events

Missing severity, relationship with study vaccine, and outcome of unsolicited AEs will not be replaced and will appear as 'UNKNOWN' in all statistical output.

9.1.3. Data derivation

When age at vaccination is to be displayed in years, it will be calculated as the number of complete calendar years between the date of birth and the date of vaccination. For example:

$$\text{DOB} = \text{PPD } 1983, \text{ Date of vaccination} = \text{PPD } \rightarrow \text{Age} = 34 \text{ years}$$

$$\text{DOB} = \text{PPD } 1983, \text{ Date of vaccination} = \text{PPD } \rightarrow \text{Age} = 35 \text{ years}$$

9.1.3.1. Temperature

Temperatures will be presented in degrees Celsius (°C). Temperatures reported in degrees Fahrenheit (°F) will be converted as follows:

$$\text{Temperature (Celsius)} = ((\text{Temperature (Fahrenheit)} - 32) \times 5)/9$$

9.1.3.2. Numerical serology results

Numerical serology results will be derived from the content of IS.ISORRES in the SDTM dataset. For assays with a specific cut-off, the following derivation rules apply:

IS.ISORRES	Derived value
"NEG", "-", or "(-)"	cut-off/2
"POS", "+", or "(+)"	cut-off
"< value" and value is <= assay cut-off	cut-off/2
"< value" and value is > assay cut-off	value
"> value" and value is < assay cut-off	cut-off/2
"> value" and value is >= assay cut-off	value
"value" and value is < cut-off	cut-off/2
"value" and value is >= cut-off	value
All other cases	missing

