## 11.6. Derived and transformed data

### Immunogenicity:

- A subject seropositive for anti-CS antibody will be a subject whose antibody concentration will be greater than or equal to the cut-off value (anti-CS  $\geq 1.9$  EU/mL).
- Seroprotection rate for anti-HBs antibody is defined as the percentage of subjects with antibody concentration greater than or equal to an established cut-off (anti-HBs  $\geq 10$  mIU/mL).
- The percentage of subjects seropositive/seroprotected and associated two-sided 95% Clopper-Pearson confidence intervals (CIs) will be computed by vaccine group for each available immunogenicity monitoring.
- The geometric mean concentrations (GMC) calculations will be performed by taking the anti-log of the mean of the log transformations. Antibody concentrations below the cut-off of the assay will be given an arbitrary value of half the cut-off of the assay for the purpose of GMC calculation.
- Handling of missing data:
  - For a given subject and a given immunogenicity measurement, missing or non-evaluable measurements will not be replaced. Therefore, an analysis will exclude subjects with missing or non-evaluable measurements.

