### Anti-HBs antibody

Anti-HBs antibody concentrations will be determined using commercially available CLIA kits ADVIA® Centaur anti-HBs2 manufactured by Siemens Healthcare. The cut-off for the assay is 6.2 mIU/mL. Results will be reported in mIU/mL.

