5.4. Immunogenicity

5.4.1. Analysis of immunogenicity planned in the protocol

The analysis of immunogenicity will be performed on the PPS for analysis of immunogenicity and efficacy.

For each group, at each timepoint where a blood sample is collected:

- The percentage of subjects with seropositive levels of anti-CS (proportion of subjects with anti-CS antibody concentrations ≥ 1.9 EU/mL) with 95% CI will be determined at specified blood sampling timepoints. Anti-CS antibody concentrations will be summarized by GMC. Anti-CS antibody concentrations will be displayed using reverse cumulative curves (RCCs). Similar analysis will be performed for the anti-full length CS protein (proportion of subjects with anti-CS antibody titers ≥ 200 1/DIL) and anti-C-term antibodies (proportion of subjects with anti-CS antibody concentrations ≥ 100 Endpoint Titer).
- The percentage of subjects with seroprotection levels of anti-HBs (anti-HBs antibody concentrations ≥ 10 mIU/mL) with 95% CI will be determined at specified blood sampling timepoints. Anti-HBs antibody concentrations will be summarized by GMC. Anti-HBs antibody concentrations will be displayed using RCCs.

Anti-CS, anti-full length CS protein and anti-CS avidity index will be summarized by mean, SD, median and quartile and box and whiskers plots will be generated.

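### SAP 9.1.3.2 stores a `< value` serology result above the assay cut-off as its upper bound, so an anti-HBs result of `<10` would be counted as seroprotected

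*SAP*

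**What the plan says.** SAP 9.1.3.2 turns reported serology into numbers: "For assays with a specific cut-off, the following derivation rules apply". Three of its rows matter here:

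- A `< value` result "and value is <= assay cut-off" becomes half the cut-off.
- A `< value` result "and value is > assay cut-off" becomes the value.
- A `> value` result "and value is < assay cut-off" becomes half the cut-off.

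Protocol Appendix A gives the anti-HBs limit: "The cut-off for the assay is 6.2 mIU/mL". The seroprotection threshold is separate, higher and inclusive. SAP 5.4.1 plans "The percentage of subjects with seroprotection levels of anti-HBs" and defines these as "anti-HBs antibody concentrations ≥ 10 mIU/mL"; Protocol 11.6 uses the same definition. For anti-CS against the repeat region, the assay cut-off and the seropositivity threshold are both 1.9 EU/mL.

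Protocol 11.6 and SAP 9.1.3.3 assign half the cut-off to concentrations below the cut-off when GMCs are calculated. Protocol 11.6 adds that "missing or non-evaluable measurements will not be replaced". Neither document has a separate rule for a `<` result whose bound lies above the cut-off.

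**The concern.** A `<` report gives only an upper bound. The second row stores that bound as if it had been measured, and classification then asks whether the stored number is at or above a threshold. When the bound equals the threshold, the answer contradicts the laboratory: a result reported as below 10 is tabulated as at least 10. When the bound exceeds the threshold, the true status is unknown but is recorded as positive. Any error from this row is upward.

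The third row has the opposite fault. A `>` report gives only a lower bound, so a bound below the cut-off does not show that the true concentration is below it.

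Anti-CS and anti-HBs concentrations are secondary endpoints. The derived values feed the seropositivity and seroprotection rates, the GMCs and the reverse cumulative curves. The anti-CS readouts also feed the SAP 5.4.2 comparisons by protection status in this study (P versus NP) and the logistic models there.

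**Working it through.** The plan gives no figure to reproduce, so the check applies the SAP 9.1.3.2 rows to example reports and then sizes the effect.

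**Inputs**
- Anti-HBs: cut-off 6.2 mIU/mL (Protocol Table 9 and Appendix A); threshold ≥ 10 mIU/mL (Protocol 11.6, SAP 5.4.1).
- Anti-CS repeat region: cut-off 1.9 EU/mL (Protocol Table 9 and Appendix A); threshold ≥ 1.9 EU/mL (SAP 5.4.1).
- Anti-C-term: cut-off 100 (Protocol Table 9 and Appendix A); threshold ≥ 100 (SAP 5.4.1).
- Group size for illustration: 20 (Protocol Table 1).

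**Step 1: apply the `<` rows**

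| Assay | Report | Stored | Scored |
|---|---|---|---|
| Anti-HBs | `<6.2` | 3.1 | not seroprotected |
| Anti-HBs | `<7` | 7 | not seroprotected |
| Anti-HBs | `<9.9` | 9.9 | not seroprotected |
| Anti-HBs | `<10` | 10 | seroprotected |
| Anti-HBs | `<20` | 20 | seroprotected |
| Anti-CS | `<1.9` | 0.95 | seronegative |
| Anti-CS | `<2` | 2 | seropositive |
| Anti-C-term | `<200` | 200 | seropositive |

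An ordinary result below the cut-off is handled correctly. Anti-HBs is miscounted only when the bound is 10 or more; a bound above 6.2 and below 10 affects the GMC but not the rate. For anti-CS and anti-C-term, any bound above the cut-off is counted as positive. For full-length CS it is unclear whether the rule applies, because Protocol Table 9 gives no cut-off, Appendix A gives 100, and SAP 5.4.1 classifies at 200.

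**Step 2: effect on a rate**

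One subject whose true value is below the threshold but who is counted as positive adds 1/20 = 5 points; two add 10. For example, 19/20 = 95% (Clopper-Pearson 75.1% to 99.9%) becomes 20/20 = 100% (83.2% to 100%). For anti-HBs `<10` the error is certain. For anti-CS `<x` with x above 1.9, 5 points per result is the most it can be.

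**Step 3: effect on an anti-HBs GMC**

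With k results stored as 10 instead of a substitute s, the GMC is multiplied by (10/s)^(k/20).
- s = 3.1 (half the cut-off): k = 1 gives (10/3.1)^(1/20) = 1.060; k = 2 gives 1.124.
- s = 5 (half the bound): k = 1 gives (10/5)^(1/20) = 1.035; k = 2 gives 1.072.

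**Step 4: would deleting the result be better?**

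Assume that the other 19 subjects have an anti-HBs GMC of 200 mIU/mL. This figure is an assumption and is not in the documents.
- Stored as 3.1: 200 × (3.1/200)^(1/20) = 162.
- Stored as 10 (current rule): 200 × (10/200)^(1/20) = 172, which is 6% above 162.
- Deleted: 200, which is 23% above 162.

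Deletion inflates the GMC more than the current rule whenever the other subjects' GMC exceeds the stored value.

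**The case against.** The strongest objection is that the triggering report may never arise. Nothing in the documents says that a laboratory will return anti-HBs `<10` or anti-CS `<x` with x above 1.9, and results below the stated cut-offs are treated properly. The `>` row needs a result bounded below the assay's own limit and may be there only for completeness. The table is also a sponsor standard (SAP 9.1), and all analyses are declared descriptive (SAP 6). All of this stands, and it limits the size of the point. It does not make the rule right: the row is written into the SAP, and nothing else there corrects it.

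Protocol 6.7.5 describes the hepatitis B correlate as above 10, under which exactly 10 would not count. The analysis definitions use 10 or more, however, and `<20` would be miscounted on either wording.

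Three stronger readings are tempting, and the documents do not support them:

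- **That the anti-HBs example distorts the correlate analysis.** SAP 5.4.2 names only anti-CS readouts in the P versus NP comparisons and lists anti-CS, full-length CS and avidity as model variables. Anti-HBs is in neither list.
- **That the `<` row contradicts Protocol 11.6.** That section deals with concentrations below the cut-off. A `<` result with a bound above the cut-off is not known to be below it, and calling it non-evaluable is an interpretation.
- **That such results should be set to missing throughout.** Step 4 shows the harm to the GMC. In addition, code 2100 in SAP 4.2.3.1 removes from the per-protocol set a subject whose anti-CS serology is not available at every visit. SAP 5.3.1 analyses efficacy on that set, so setting anti-CS results to missing could cost challenged subjects in the primary analysis.

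**Conclusion.** The point holds as a minor defect. As written, SAP 9.1.3.2 would count anti-HBs `<10` as seroprotected, which the laboratory report rules out. It would also count anti-CS `<x` with x above 1.9 as seropositive, and score a `>` result below the cut-off as negative, in both cases without evidence.

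At 20 per group, the size is up to 5 points on a rate per result, and about 6% on an anti-HBs GMC per `<10` result against a substitute of 3.1 (about 4% against 5). The number of such results is not given and may be zero, in which case there is no effect. The reach is limited to descriptive immunogenicity summaries and, for anti-CS readouts only, the exploratory analyses by protection status. The primary smear endpoint is not touched by the rule.

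**What to change.** Amend SAP 9.1.3.2 so that classification and numerical substitution are separate.

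- **Rates, `< value` above the cut-off:** score as below threshold when the value is at or below the classification threshold. Score as indeterminate, meaning missing for that rate only, when the value is above it.
- **Rates, `> value` below the cut-off:** score as indeterminate instead of negative.
- **GMCs and models:** keep `<` results. Use a substitute below the reported bound, for example half the cut-off as in the SAP's existing convention, or a censored-data likelihood. Repeat with the upper bound as a sensitivity analysis, since half the cut-off is itself arbitrary when the bound is higher.
- **Analysis set:** state that a censored anti-CS result counts as available for elimination code 2100, so that the per-protocol set used for primary efficacy does not change.

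The cost is a few lines in the SAP and a small study-level change to the sponsor's standard derivation program. A rare result becomes indeterminate for a rate, with little loss of precision: with every other subject positive, 19/19 has an exact lower limit of 0.025^(1/19) = 82%, against 0.025^(1/20) = 83% for 20/20. Fixing the rule in advance also avoids deciding on individual sera after the results are known.

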9.1.3.3. Geometric mean concentrations (GMCs)

Geometric Mean Concentration (GMC) calculations are performed by taking the inverse logarithm of the mean of the log concentration transformations. Antibody concentrations below the cut-off of the assay will be given an arbitrary value of half the cut-off of the assay for the purpose of GMC calculation. The cut-off value is defined by the laboratory before the analysis and is described in the protocol.

9.1.3.4. Onset day

The onset day for an event (e.g. AE, medication, vaccination) is the number of days between the study vaccination and the start date of the event. This is 1 for an event occurring on the same day as a vaccination (and reported as starting after vaccination).

9.1.3.5. Duration of events

The duration of an event with a start and end date will be the number of days between the start and end dates plus one day, i.e. an event that starts on 03MAR2018 and ends on 12MAR2018 has a duration of 10 days.

The duration of solicited events will be calculated as the sum of the individual days with the symptom reported at grade 1 or higher.

9.1.3.6. Counting rules for combining solicited and unsolicited adverse events

For output combining solicited and unsolicited AEs, all SAEs will be considered general events since the administration site flag is not included in the expedited adverse event CRF pages.

Multiple events with the same preferred term which start on the same day are counted as only one occurrence.

9.1.3.7. Counting rules for occurrences of solicited adverse events

When the occurrences of solicited AEs are summarized, each event recorded as having occurred during a specific period will be counted as only one occurrence regardless of the number of days on which it occurs.

9.1.4. Display of decimals**9.1.4.1. Percentages**

Percentages and their corresponding confidence limits will be displayed with:

- no decimals when there are fewer than 50 subjects in each tabulated group
- one decimal when there are at least 50 subjects in at least one tabulated group

- Exceptions will be made for percentages that are not 0% or 100% but appear as 0% or 100% due to rounding. For these specific cases the number of decimals will be increased until the displayed value is no longer 0% or 100%. Examples are given in the following table.

n/N	Displayed percentage
10/45	22%
1/45	2%
10/55	18.2%
1/55	1.8%
1/300	0.3%
1/3000	0.03%
1/30000	0.003%
299/300	99.7%
2999/3000	99.97%
29999/30000	99.997%

- The display of additional decimals for values close to 0% or 100% will be applied only to point estimates and not confidence limits, which can be rounded and displayed as 0% or 100%.
- Values of exactly 0% or 100% will be presented with no decimals regardless of the number of subjects per tabulated group.

9.1.4.2. Differences in percentages

Differences in percentages and their corresponding confidence limits will be displayed with one more decimal than the maximum number used to display the individual percentages, for example the difference between two percentages displayed with one decimal will be displayed with two decimals.

9.1.4.3. Demographic/baseline characteristics statistics

The mean, median, and SD for continuous baseline characteristics (height, weight, body mass index (BMI), pre-vaccination body temperature) will be presented with one decimal.

The minimum and maximum values and quartile values (if required) will be presented with the same number of decimals as the observed values.

The maxima and minima of transformed height variables will be displayed with no decimals.

The maxima and minima of transformed weight variables will be displayed with no decimals with the exception of values below 10kg where one decimal will be displayed.

The maximum and minima of transformed body temperatures will be displayed with one decimal.

9.1.4.4. Serological summary statistics

The number of decimals used when displaying geometric mean concentrations (GMC) and their confidence limits is shown in the following table:

GMC value	Number of decimals to display
<0.1	3
≥0.1 and <10	2
≥10 and <1000	1
≥1000	0

When multiple categories of GMC values are present in the same table, the number of decimals displayed should match that of the smallest category (i.e. the one with the higher number of decimals). For example, if GMC values of <0.1 appear in the same table as values of ≥0.1 and <10, 3 decimals should be displayed for both.

GMC ratios and their confidence limits will be displayed with 2 decimals regardless of the actual values.

9.1.5. Statistical methodology

9.1.5.1. Exact confidence intervals around proportions

The exact CIs around within-group proportions are derived using the method of Clopper and Pearson [[Clopper](#), 1934].

9.1.5.2. Standardized asymptotic confidence intervals around differences in proportions

The standardized asymptotic confidence intervals around differences in proportions are derived using the method of Miettinen and Nurminen [[Miettinen](#), 1985].

9.1.5.3. Adjusted GMC ratios

When between-group GMC ratios are computed and adjusted for two-level categorical co-variables, these co-variables should be included as dummy continuous variables in the SAS procedure.

9.2. TFL and/or TFL ToC

The TFL and/or the TFL ToC can be found in eTMF folder section 11.1.1.

